8.2. Secondary Analysis

The effects of the sociodemographic and medical history factors on the primary outcome will be analyzed using the Poisson regression model. A standard regression results table will be presented to indicate which, if any, of these factors are significant influencers.

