For the intervention arm, participants will be given the consent form. After having consented to participate in the study, they will be given the socioeconomic and health history form. In what follows, they will receive a 30-minutes brief about the mobile app HERA and will be asked to download it. The mobile application will automatically plan out the dates of further prenatal care appointments based on the date of the last menstruation. Participants will receive reminders in the form of push notifications for prenatal checkup dates for 6 months. Reminders will be sent at the following intervals: 1) 2 weeks before, 2) 1 day before and 3) on the day of the recommended appointment. After the recommended appointment date, participants will receive push notifications asking whether or not they went to the appointment in weekly intervals for 1 month. This reminder algorithm will be used for each prenatal checkup for a total of three appointments post the baseline visit: once in second trimester and two in third trimester, using the World Health Organization and Turkish Ministry of Health prenatal checkup calendar. At the end of 6 months of follow up time, participants in the intervention arm will be contacted via phone call to ask for any remaining appointments or unanswered notifications. Completeness of 3 prenatal care appointments post the baseline visit, as recommended by WHO and implemented by Turkish MoH will be compared to the control groups.

Participants in the informed control arm will be given the consent form and will be asked for their contact information if consented. They will also be given the socioeconomic and health history form. Participants in the non-informed control group just will be given the socioeconomic and health history form. Both the informed and non-informed control group members will be

reached out at the end of the 6-month study period to be asked about the number of prenatal care appointments they attended. If unable to be reached, retrospective chart review of the participant's medical record will be attempted, in order to obtain the number of attended prenatal care appointments.

6. 2. 1. Recruitment Strategy

Participants will be enrolled from the obstetrics and gynecology department of refugee health clinics in Istanbul, Turkey with the help of a translator (Turkish to Arabic). The enrollment will take place with the help of the physician.

6. 3. Study Population

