The population included in this study are pregnant Syrian refugee women between the ages of 18 to 49, who are in their first trimester of pregnancy.

6. 3. 1. Eligibility

Inclusion Criteria:

- Having the status of “Syrian under temporary protection”
- Being in the first trimester of the pregnancy
- Initial prenatal visit
- Age equal or greater than 18 years and less than or equal to 49

Exclusion Criteria:

- Having a citizenship or a status other than “Syrian under temporary protection”
- Not owning a mobile phone
- Being unable to read and write
- Not initial prenatal visit
- Having a chronic disorder or high-risk pregnancy that requires the individual to go to the hospital frequently. Frequently is defined as more than 3 visits post the baseline visit.
- While gestating, those that develop a high-risk pregnancy that requires more than 3 visits post the baseline visit.

6. 4. Sample Size Determination

The primary outcome measure for the power and size calculation is the difference in the mean number of visits among the different arms of the study. We set our target detectable difference in means to be 0.5 or more additional visits. As the maximum standard deviation is 1.5 due to the restricted range of 0 to 3 visits, our target effect size is $0.5/1.5 = 0.33$. Our calculation shows that each arm will need at least 40 patients to have a power of 90% and a two tailed significance level of 0.05. Due to the nature of refugees, we anticipate a high loss due to follow up and other reasons for dropout. Without prior information, we assume a 20% loss rate and therefore inflate the number of patients per arm by 25%. Thus, we plan to enroll 54 patients per arm for a total of 162 individuals. The statistical software G*Power Version 3.1.9.6 available from the UCLA Institute for Digital Research & Education Statistical Consulting website; [G*Power \(ucla.edu\)](http://G*Power (ucla.edu)), was used for the calculations.

6. 5. Randomization Strategy

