Subjects will be selected on the following basis: randomly select a week and recruit on 6 days of that week. On 3 of the days the selection process will start in the morning, denoted as AM, (the first part of the day that is expected to see half of the patients) and on the other 3 days the selection process will start in the afternoon, denoted as PM, (the second part of the day that is expected to see half of the patients.) For each AM/PM session, the first 27 subjects giving approval to be in the study will be randomly assigned into one of the 3 arms. It is estimated that 100 to 200 women use the hospital daily. Thus, we feel that most likely the daily target intakes will be met. However, if not met by the end of the AM/PM shift, the selection process will stop. After day 6 and before any data analysis, a check will be done on the sample sizes and additional subjects may be recruited by selecting another week to perform additional recruiting.

This sampling plan requires that the number of women coming to see the medical staff be approximately the same day to day and AM to PM.

Details of the random assignment to AM/PM and to groups are attached. The assignment of treatment and control groups to 0, 1 or 2 will be done prior to the start of subject recruitment but will not be shared with the data analyst until after the analysis is complete.

7. Outcomes

Primary Outcome:

The primary outcome of this study is the number of medical visits, following the initial baseline PNC visit, over the 6-month period prior to childbirth.

Secondary analyses:

In the secondary analyses, we will further examine other risk factors, including sociodemographic and reproductive medical history, on the number of medical visits during the study period. The following additional data will be gathered:

1. Age
2. Highest level of education
3. Current employment status and profession if employed
4. Marital status
5. If married, whether the spouse is alive or deceased
6. If married, whether the spouse resides with the participant or not
7. Number of children
8. Ages of children
9. Miscarriage history, and the number and the timing of miscarriage, if any
10. Number of deceased children, if any
11. Number of times the participant gave birth to stillborn baby, if any
12. If prior pregnancies, the number of deliveries occurred at home and at a hospital
13. Type of delivery (vaginal, C-section) and the number of each type

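### SAP 8.2 relies on model-based Poisson standard errors for a 0–3 visit count, so the p-values in the risk-factor table may be miscalibrated in either direction.

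*Combined protocol and SAP*

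**What the plan says.** SAP 8.2 (Secondary Analysis) is the only method stated for the risk-factor analyses. The effects of the listed factors "will be analyzed using the Poisson regression model", and then "A standard regression results table will be presented to indicate which, if any, of these factors are significant influencers". SAP section 8 names no dispersion check, quasi-likelihood, robust variance or alternative model.

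The outcome is the primary one, which SAP section 7 defines as "the number of medical visits, following the initial baseline PNC visit, over the 6-month period prior to childbirth". SAP 6.4 (Sample Size Determination) gives its range: "As the maximum standard deviation is 1.5 due to the restricted range of 0 to 3 visits". SAP 6.2 (Study Procedure) plans the reminders "for a total of three appointments post the baseline visit: once in second trimester and two in third trimester". SAP 6.3.1 (Eligibility) excludes women whose chronic disorder or high-risk pregnancy calls for frequent attendance: "Frequently is defined as more than 3 visits post the baseline visit".

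**The concern.** A Poisson count has no upper limit, and its variance equals its mean. A count of at most three scheduled visits satisfies neither condition in general. The ordinary Poisson output takes its standard errors from the mean alone, so it does not respond when the observed spread is smaller or larger than assumed.

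The stated product of this analysis is a judgement of significance, factor by factor. If the standard errors are too large, real influences on attendance are missed. If they are too small, chance associations are reported as influences. The SAP contains no step that would show which of these has happened.

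**Working it through.** **Inputs.** Range 0 to 3 and maximum SD 1.5 (SAP 6.4). Total enrolment 162 and assumed loss 20% (SAP 6.4), so 162 × 0.80 = 129.6, about 130 women. Target difference: "We set our target detectable difference in means to be 0.5 or more additional visits" (SAP 6.4). The documents give neither the attendance probability p nor the correlation ρ between one woman's visits, so both are assumptions, shown as a range.

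**The plan's own figure.** The largest SD on a 0–3 range is (3 − 0)/2 = 1.5, as stated. It is reached only with half the women at 0 and half at 3: mean 1.5, variance 2.25.

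**The upper limit.** A Poisson variable with mean 1.5 puts 6.6% of its probability above 3; with mean 2 the figure is 14.3%.

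**Standard errors.** Let φ = variance/mean. The ratio of the Poisson standard error to the true one is 1/√φ, and the actual size of a nominal 5% test is 2 × [1 − Φ(1.96/√φ)]. For a 0–3 count the variance is at most mean × (3 − mean), so φ ≤ 3 − mean. Above mean 2, φ is therefore below 1 and the standard errors are too large. Below mean 2, either direction is possible.

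If each of three visits has attendance probability p and pairwise correlation ρ, the mean is 3p, the variance is 3p(1 − p)(1 + 2ρ), and φ = (1 − p)(1 + 2ρ). The simulation column uses 130 women and one balanced binary factor with no effect.

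| Assumed attendance | Mean | Variance | φ | SE ratio | Size, formula | Size, simulated |
|---|---|---|---|---|---|---|
| p = 0.5, ρ = 0 | 1.5 | 0.75 | 0.50 | 1.41 | 0.6% | 0.5% |
| p = 0.67, ρ = 0 | 2.0 | 0.67 | 0.33 | 1.73 | 0.07% | under 0.1% |
| p = 0.5, ρ = 0.2 | 1.5 | 1.05 | 0.70 | 1.20 | 1.9% | about 2% |
| p = 0.4, ρ = 0.3 | 1.2 | 1.15 | 0.96 | 1.02 | 4.6% | about 5% |
| p = 0.5, ρ = 0.5 | 1.5 | 1.50 | 1.00 | 1.00 | 5.0% | about 5% |
| All or none, mean 1.5 (SD 1.5) | 1.5 | 2.25 | 1.50 | 0.82 | 11.0% | about 11% |
| All or none, mean 2 | 2.0 | 2.00 | 1.00 | 1.00 | 5.0% | about 5% |
| All or none, mean 2.25 | 2.25 | 1.69 | 0.75 | 1.15 | 2.4% | about 2% |

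With robust standard errors the simulated size was about 4% to 5% in these scenarios.

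**Power for a 0.5-visit factor** (p = 0.50 against 0.67, means 1.5 and 2.0, 65 women per level). The log ratio of means is ln(2.0/1.5) = 0.288. The Poisson standard error is √[1/(65 × 1.5) + 1/(65 × 2.0)] = 0.134, so significance needs an estimate above 1.96 × 0.134 = 0.263.

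- Independent visits: the true standard error is √[0.50/97.5 + 0.333/130] = 0.088. Model-based power is Φ[(0.288 − 0.263)/0.088], about 61%. With a correct standard error it is Φ(0.288/0.088 − 1.96), about 91%. Simulation gives about 62% and 92%.
- ρ = 0.2: the true standard error is 0.088 × √1.4 = 0.104. The same formulas give about 60% and 79%; simulation gives about 60% and 80%.

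**The case against.** The strongest reply is that the error is conditional. One woman's visits are plausibly correlated, and moderate correlation can bring the variance close to the mean: at p = 0.4, ρ = 0.3 the test is nearly exact. This stands. A reader might infer that the p-values are bound to be wrong, but the documents give no visit distribution, so they do not support that. Exact calibration needs ρ = p/[2(1 − p)], which is 0.5 at p = 0.5 and a perfect 1.0 at p = 0.67. It can happen, but the plan has no step to check it.

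A reader might also infer that all-or-none attendance always makes the standard errors too small. It does so only below a mean of 2 visits; at mean 2 they are right, and above it they are too large.

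The bound is also less settled than SAP 6.4 suggests. SAP section 7 and the protocol's Detailed Description state no cap, the protocol's Outcome Measures count four mandatory appointments, and the eligibility rule does not limit attendance by women at ordinary risk. This also stands. It weakens the case for binomial regression out of 3, but not the case for a variance estimated from the data, which is valid with or without a cap.

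Finally, the analysis is secondary, with no power claim attached. The coefficients can still be read as log ratios of means if the mean model is right, and the SAP's wording does not forbid robust standard errors. All of this is true and limits the consequence. But significance is what the table is meant to report, and no protection is specified.

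**Conclusion.** The point holds as an unprotected analysis choice, not as a certain error. For an outcome limited to 0 to 3, model-based Poisson standard errors are right only if the variance happens to equal the mean. They are too large whenever the mean exceeds 2 visits, and can err either way below that.

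Under the assumed distributions, a nominal 5% test has a true size between under 0.1% and about 11%; the upper figure is at the SD that the plan itself used for sizing. The power loss for a 0.5-visit factor is about 30 percentage points if visits are independent and about 20 at a correlation of 0.2. These sizes rest on 130 analysed women, one balanced binary factor, and values of p and ρ that the documents do not supply.

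Only the secondary risk-factor table is affected. A reader might infer that the trial's main comparison is also compromised; it is not, because the one-way ANOVA in SAP 8.1 does not use the Poisson assumption.

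**What to change.** In SAP 8.2, keep the log-link model for the mean and add one sentence: standard errors, confidence intervals and p-values will be robust (sandwich) or dispersion-scaled (quasi-Poisson). State in advance which of the two will be used.

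Confirm whether the outcome is the number attended out of three scheduled visits after baseline. If so, quasi-binomial regression out of 3 is a reasonable alternative. If more than three visits can be recorded, keep the log-link model with the corrected variance.

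The cost is a sentence in the SAP and a standard option in R, with no new data. Intervals will become narrower or wider according to the observed spread. If the variance does prove close to the mean, little changes.

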14. Information on prenatal care appointments made during prior pregnancies, and the number of appointments attended
15. Information on medical conditions that require long-term medication use, if yes, the name of the condition and medication
16. Duration of time living in Turkey

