Recruitment strategy: Participants will be enrolled from the obstetrics and gynecology department of refugee health clinics in Istanbul, Turkey with the help of a translator (Turkish to Arabic). The enrollment will take place with the help of the physician.

Primary Outcome: The primary outcome of this study is the number of medical visits, following the initial baseline PNC visit, over the 6-month period prior to childbirth.

Secondary outcomes: Secondary outcomes are based on the Sociodemographic and Health History form. The form gathers information about demographics of the participants (age, education, employment, marital status, number of children) and health history (previous pregnancies, delivery methods, miscarriages, stillborn, chronic conditions and medications. We will further examine these risk factors on the number of medical visits during the study period.

Conditions

Conditions: Prenatal Care, Pregnancy

Keywords: Mobile health, Refugee

Study Design

Study Type: Interventional

Primary Purpose: Health Services Research

Interventional Study Model: Parallel Assignment

The intervention group cluster will use the HERA application to receive appointment reminders. The Informed and Non-Informed Control groups will not be using the HERA application.

Number of Arms: 3

Masking: None (Open Label)

Allocation: Randomized

Enrollment: 162 [Anticipated]

Arms and Interventions

Experimental: Reminder

Participants will fill the sociodemographic and health history form. Participants will receive reminders in the form of push notifications for prenatal checkup dates automatically generated according to their pregnancy start data or initial check-up appointment for 6 months. Reminders will be sent at the following intervals: 1) 2 weeks before the appointment, 2) 1 day before the appointment, and 3) on the day of appointment. After this date, participants will receive push notifications asking whether they went to the appointment or not weekly for 1 month. This reminder algorithm will be used for each prenatal checkup for a total of four appointments: once in first trimester, once in second trimester and two in third trimester, using the World Health Organization and Turkish Ministry of Health prenatal checkup calendar. At the end of 6 months of follow up period, participants will be contacted via phone call to ask for any remaining appointments or unanswered notifications.

No Intervention: Informed Control No Reminder

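### SAP 8.2 names significant influencers from up to 16 listed items with no error control, exploratory label or arm term; the false-hit rate is 56% under ideal 5% tests and otherwise depends on the variance of the visit count.

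*Combined protocol and SAP*

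**What the plan says.** SAP section 8.2 names the model and its terms: "The effects of the sociodemographic and medical history factors on the primary outcome will be analyzed using the Poisson regression model". It then gives the reading rule: "A standard regression results table will be presented to indicate which, if any, of these factors are significant influencers". Arm is neither named as a term nor expressly left out.

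The factors come from SAP section 7, under secondary analyses, where "we will further examine other risk factors, including sociodemographic and reproductive medical history, on the number of medical visits during the study period". A numbered list of data to be gathered follows, ending at "16. Duration of time living in Turkey". The protocol's Detailed Description (secondary outcomes) has a shorter list: "demographics of the participants (age, education, employment, marital status, number of children) and health history", the latter covering five or six topics, so about 10 to 11 in all.

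Neither document gives a significance level for this analysis, a multiplicity rule or an exploratory label. The only level stated is in the sample-size section (SAP 6.4): "a power of 90% and a two tailed significance level of 0.05".

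**The concern.** A regression table with many coefficients, read for whichever are significant, tends to produce chance findings. Here the hits would be called influencers, a causal word for observational associations in about 130 women (162 less the assumed 20% loss is 129.6), analysed as complete cases under SAP 7.1. A chance finding could then be reported as a driver of refugee women's attendance.

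Arm also belongs in the model. Only one arm gets reminders, and visits are ascertained differently. Under SAP 6.2 the intervention arm gets weekly app prompts after each appointment date and a closing call, while controls are contacted once at the end, with chart review as back-up. SAP 6.1 instead says that the third arm's data come retrospectively from hospital records. On either account the arms differ in how visits are counted.

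**Working it through.** **Plan's own figure.** The documents give no error rate for this table. Their one computed design figure, 40 per arm, reproduces when 0.33 is entered as Cohen's f in a three-group ANOVA (power 0.902 at 40, 0.894 at 39). Whether that is the right entry is a separate matter; here it only supplies n = 3 × 40 = 120 for the simulations.

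**Inputs**
- 16 items (SAP 7); about 10 to 11 topics (protocol, Detailed Description).
- Two-sided 0.05, carried over from SAP 6.4 by assumption.
- Count range and SD (SAP 6.4): "As the maximum standard deviation is 1.5 due to the restricted range of 0 to 3 visits".
- Arm effect (SAP 6.4): "We set our target detectable difference in means to be 0.5 or more additional visits".
- Mean of 1.5 visits: assumed, the midpoint of 0 to 3. The documents give no mean.

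**Step 1: calibrated, independent, all-null tests.** The chance of at least one false hit in k tests is 1 − 0.95^k.

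| k | Chance |
|---|---|
| 10 | 40.1% |
| 11 | 43.1% |
| 13 | 48.7% |
| 14 | 51.2% |
| 16 | 56.0% |

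With 16 tests, 16 × 0.05 = 0.8 false hits are expected.

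**Step 2: the planned Poisson tests on a 0 to 3 count.** Let φ = variance/mean. A nominal 5% Poisson Wald test has true size of about a = 2[1 − Φ(1.96/√φ)], and the rate for 16 tests is 1 − (1 − a)^16. At mean 1.5:

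| Visits | φ | a | 16 tests |
|---|---|---|---|
| Binomial, 3 visits at 50% (variance 0.75) | 0.50 | 0.56% | 8.6% |
| SD 1.0 (variance 1.0) | 0.67 | 1.64% | 23% |
| Evenly spread over 0 to 3 (variance 1.25) | 0.83 | 3.2% | 40% |
| Variance equal to mean | 1.00 | 5.0% | 56% |
| SAP maximum SD 1.5 (variance 2.25) | 1.50 | 11.0% | 84% |

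The 16-test rate passes 50% only when φ exceeds about 0.93.

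**Step 3: simulation.** Poisson models with 16 null factors (2,000 runs each, n = 120 and 162) gave about 8% for binomial visits, 39% to 42% for visits spread over 0 to 3, 83% to 84% at maximum SD, and 53% to 56% for true Poisson counts. Correlating the factors at 0.5 with true Poisson counts (n = 120) gave 52%. With quasi-Poisson tests, which correct the dispersion, the rate was 42% to 54% across all settings.

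**Step 4: arm.** For arm means (m + 0.5, m, m) in equal arms, the between-arm variance is 0.5² × (1/3)(2/3) = 0.0556. That is 0.0556/2.25 = 2.5% of the variance at SD 1.5, and 0.0556/1.0 = 5.6% at SD 1.0. In simulation with this arm effect (n = 120), the false-hit rate without and with an arm term was 57% and 55% (Poisson), 7% and 5% (binomial), and 79% and 77% (near-maximum SD).

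**The case against.** A reader might infer that a false influencer is more likely than not. The documents do not support that. It needs at least 14 independent null tests, each at a true 5%. Section 8.2 states no level, and SAP 7 introduces its list as data to be gathered, not as fixed model terms. Some items apply only to married women or to those with earlier pregnancies; others, such as education, would give several coefficients. If some factors truly matter, fewer nulls remain. The planned Poisson tests could also be far more conservative than 5%. This part of the objection stands, so the 56% must carry its conditions.

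A reader might also infer that omitting arm produces the false influencers. It does not. Arm is described as randomized, so baseline factors are independent of it in expectation, and chance imbalance is already part of each test's error rate. The shift is about 2 percentage points.

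Finally, the analysis is secondary, the primary ANOVA does not depend on it, and formal adjustment of a risk-factor table is a matter of judgement. On uncorrected Poisson p-values, adjustment would not deliver what it promises. A Bonferroni threshold for 16 tests (0.05/16 = 0.0031) still gives a familywise rate of about 22.5% at φ = 1.5, and only about 0.05% at φ = 0.5. That too stands, and is why adjusted p-values are optional below.

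What the objection leaves untouched is the reading rule itself. The low rates arise only where the Poisson variance is too large for the data, which is a fault of its own. With the dispersion corrected, the simulated rate returned to 42% to 54%.

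**Conclusion.** The concern holds in a conditional form. Section 8.2 declares influencers from a table of up to 16 listed items without a stated level, error control or exploratory label, and names no arm term.

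- **False hits:** 56% for 16 tests and 40% to 43% for 10 to 11, if all factors are null and independent and each is tested at a true 5%. For plain Poisson tests on a 0 to 3 count, 16 tests at an assumed mean of 1.5 give about 8% to 84%, depending on a variance that the documents bound but do not otherwise give.
- **Arm:** a small precision and specification gap, 2.5% to 5.6% of the variance for a 0.5-visit effect. This assumes randomization as described and losses that do not tie arm to the baseline factors.

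The primary comparison is unaffected.

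**What to change.** In SAP 8.2:

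1. Add arm as a model term (2 degrees of freedom), and state which listed items enter and how they are coded.
2. Use standard errors suited to a bounded 0 to 3 count: quasi-Poisson, robust, or a binomial model.
3. Label the table exploratory and report every estimate with a 95% CI.
4. Replace the reference to significant influencers with *factors associated with the number of visits*.

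Multiplicity-adjusted p-values (Holm or Benjamini-Hochberg) are optional, and useful only once item 2 is in place.

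The cost is a few sentences of SAP text and a small change to the R model call; no new data are needed. The downside is fewer or weaker claims about individual factors.
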